## 6.2 Units and Precision

No intermediate rounding is performed in SDTM datasets; only final values for TFLs are rounded as follows. Immunogenicity titers are reported with one decimal place or two significant digits (e.g., 0.032, 18.0). Ratios of GMTs are presented with two decimal places.

Vital sign data are reported using standard international units. Vital signs variables including derivations thereof are reported to the same precision as the source data. Parameters derived directly from source data (e.g., minimum, maximum) or first-order statistics (e.g., mean) are reported and analyzed with the same precision as the source data. Second-order statistics (e.g., SD) are reported with one more significant digit than the source data. Percentages are reported to one decimal place.

## 6.3 Derived Variables

This section provides definitions of the derived variables. In some cases, the definitions are provided in the relevant sections as noted.

**AE, causing study discontinuation**, is defined as a Yes response to the corresponding question on the AE eCRF.

**AE, medically attended (MAAE)**, is defined as a Yes response to the corresponding question on the AE eCRF.

**AE, related**, is defined as one that is “probably” or “possibly” related to IP per investigator assessment on the eCRF. If the relationship is missing for one or more occurrences of an AE for a given participant, the closest relationship of the remaining occurrences of the AE for that participant is used; if the relationship is missing for the only occurrence of an AE for a given participant, then that event is assumed to be related in order to be conservative.

**AE, resulting in death**, is defined as a Yes response to the corresponding question on the AE eCRF and/or a fatal outcome.

**AE, serious**, is defined per the derived eCRF field for AE seriousness, based on the individual criteria that make an AE qualify as serious (results in death, is life-threatening, requires inpatient hospitalization or prolongation of existing hospitalization, results in persistent or significant disability/incapacity, or is a congenital anomaly or birth defect, or any event that may require medical or surgical intervention to prevent one of these outcomes).

**AESI** is defined in this study as new onset or worsening arthralgia that is medically attended, as noted by an AE having a Yes response to the corresponding AESI question on the AE eCRF.

**AE, severity**, is graded Grade 1 (mild) to Grade 4 (potentially life-threatening) as described in Section 5.9. If the severity is missing for one or more occurrences of an AE for a given participant, the maximum severity of the remaining occurrences of the AE for that participant is used; if the severity is missing for the only occurrence of an AE for a given participant, then that event is assumed to be severe in order to be conservative.

**AEs, solicited**, are defined as those collected in the electronic e-diary or paper diary. Solicited AEs include local (i.e., pain, redness, and swelling) and systemic reactions (i.e., fever, chills, fatigue, headache, myalgia, arthralgia, and nausea). *Solicited AEs were to be entered on Day 1 through Day 8; solicited AEs starting on Day 9 or later will be excluded from tabulations, with the exceptions of AESI and SAEs (see Section 9.2.2 for solicited events collection details).*

The denominator for solicited AE tables comprises only those participants with at least one diary observation (i.e., any non-missing values but excluding “Not done/unknown”), at least one diary observation for a given symptom, or at least one diary observation for a given day, as applicable. *Note that an elevated in-clinic temperature assessment as part of 30-min post-vaccination vital signs does not count as a solicited AE, as vital signs data are summarized separately.*

**AE, treatment emergent**. AE collection begins at Day 1 (baseline), the day of IP administration. AEs occurring after a participant has given informed consent, but before vaccination, are excluded from summaries. Only treatment-emergent AEs are summarized.

**AEs, unsolicited**, are defined as those AEs not listed in the e-diary or paper diary but collected in the EDC. *Unsolicited AEs were to be collected though Day 29 unless they were SAEs, AESI, or MAAEs; unsolicited AEs starting on Day 30 or later that are not SAEs, AESI, or MAAEs are excluded from tabulations (see Section 9.2.2 for solicited vs. unsolicited events).*

Age at screening visit is automatically calculated by EDC based on date of birth versus date of informed consent. Age at baseline (Day 1) is be summarized in all outputs.

**Age group strata** are defined as ages  $\geq 65$  to  $< 75$  and  $\geq 75$  years as randomized. Note that, if a participant is randomized into a stratum and their age is later corrected such that they

should have been placed into a different age stratum, the participant is analyzed according to the corrected age stratum for immunogenicity analyses.

**Analysis visits** are defined in Section [5.5](#).

**Analysis populations** are defined in Section [5.3](#).

**Baseline** is defined in Section [5.6](#). Change from baseline is defined as (value at post-baseline assessment – value at baseline).

**Baseline seropositive rate** is defined as the percentage of participants with anti-CHIKV human SNA assay titer  $\geq$ LLOQ prior to IP administration.

**Body mass index** at screening visit is automatically calculated by EDC as a participant's weight in kg divided by height in  $\text{m}^2$ .

**Anti-chikungunya virus (anti-CHIKV) human SNA assay NT80 (80% neutralizing titer)** is defined as the dilution factor that corresponds to an 80% reduction of luciferase activity compared to virus-only control. Anti-CHIKV SNA titer values below LLOQ are replaced by LLOQ/2 in the immunogenicity analyses including GMT and GMFI. For the 4-fold rise over Day 1 (baseline), values below the LLOQ are replaced with the LLOQ.

**Completion of study** for an individual participant is defined as completion of the Day 183 EOS and any required safety follow-up (i.e., a disposition status of completed).

**Early discontinuation** for an individual participant is defined as completion of the Early Discontinuation/ Withdrawal Visit (i.e., a disposition status other than completed).

**Enrolled/randomized** is defined as receipt of a randomization number assignment within the EDC system.

**Medical history** items entered on the medical history eCRF are considered to predate the study regardless of onset date.

**Medication, concomitant**, is defined as one taken after start of IP administration on Day 1 (baseline) through the end of study. For analysis purposes, any medication which is ongoing or with a stop date that is on or after the start date of IP administration is categorized as a concomitant medication. Partial or missing concomitant medication start and/or end date are imputed according to Section [6.5.2](#).

**Medication, prior**, is defined as one with a stop date within 30 days prior to the screening visit (90 days for blood products) through the start of IP administration on Day 1 (baseline).

**Protocol deviations** are defined by inclusion in the EDC protocol deviation module (participant-level only, not site-level), including monitor-identified deviations as well as Sponsor- and EDC system-identified programmatic deviations. Protocol deviations are classified by category and type (important/not important).

**Randomized participant not meeting entry criteria** is defined using the protocol deviation dataset and not just the inclusion exclusion criteria dataset, because a project team decision was made to keep the inclusion exclusion criteria as entered at the time of randomization even if the participant was later found to have violated entry criteria. These violations are recorded as protocol deviations.

**Rounding of values** is described in Section 6.2.

**Seroresponse rate** is defined as the percentage of participants who achieve an anti-CHIKV SNA titer █.

**Study Day 1** is defined as the day of IP administration on Day 1 (baseline). The day prior to Day 1 is Day -1. There is no Day 0. If the participant is not treated, then the Day 1 (baseline) is defined as the day of randomization.

Study day relative to Day 1 are calculated as:

- **Study Day** = (assessment date – date of Day 1 + 1) if the assessment is on or after Day 1.
- **Study Day** = (assessment date – date of Day 1) if the assessment is before Day 1.

For conversion of durations, 1 year = 365.25 days and 1 month = 365.25/12 = 30.4375 days.

**Subgroups** for sex (male and female), race (white and non-white) and ethnicity (Hispanic or Latino and Not Hispanic or Latino) are defined based on the corresponding demographic questions. Participants missing sex, race or ethnicity will be omitted from analyses by subgroup. Participants with “Not Reported” or Unknown” ethnicity are not included in ethnicity subgroups.

**Summary statistics** are described in Section 6.1.

**Time duration (in days) between event A and event B** is (date of event B – date of event A + 1). For conversion of durations, 1 year = 365.25 days and 1 month = 365.25/12 = 30.4375 days.

**Treatment, actual**, is defined as the treatment administered to the participant by the site (i.e., corresponding to the kit number used).

**Treatment group** is defined as PXVX0317 vaccine vs. placebo.

**Treatment, randomized**, is defined as the treatment assigned to the participant by the EDC (i.e., corresponding to the kit number assigned).

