3.2.9 Assess Solicited Adverse Events

Electronic or paper diaries (memory aids) will be used to collect solicited AEs following vaccination. Participants will record events in their diary daily, for at least seven days after vaccination. Solicited AEs to be assessed in this study are local events of pain, redness, and swelling at the injection site and systemic events of oral temperature $\geq 38.0^{\circ}\text{C}$ ($\geq 100.4^{\circ}\text{F}$), chills, fatigue, headache, myalgia, arthralgia, and nausea.

Participants will be trained to complete a diary (electronic or paper) to observe, measure, and record these solicited AEs daily. A digital thermometer will be provided to the participants to measure their temperature each day. The highest temperature measured each day should be recorded in the participant's diary or memory aid (electronic or paper). To record injection site local reactions, a ruler will be provided to the participant to measure and record the diameter of redness and swelling at the largest point of the reaction each day.

Study staff will review the signs and symptoms recorded in the diary or memory aid (electronic or paper) daily and will follow-up with participants if any data is missing. The investigator will then assess all solicited AEs for severity (Section 8.1.8) and the action taken, and causality (Section 8.1.9). The results of the investigator's assessment will be recorded as a separate source document and will be entered on the solicited AE eCRF.

Symptoms continuing beyond the solicited AE collection period will be collected and recorded on the AE eCRF.

Details on safety definition, evaluation, reporting periods and documentation are outlined in Section 8.

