8.1.9 Causality of Adverse Events

The investigator is responsible for the assessment of the causality of an AE and the sponsor's MM will also assess SAE causality, independent of the PI.

The following guidelines are provided for this assessment:

[figure not shown]
- **Unrelated:** No relationship between the IP and the reported event. The event will be considered “not related” to the IP.
- **Possibly related:** The event follows a reasonable temporal sequence from the time of administration of IP and/or follows a known response pattern to the IP but could also have been produced by other factors.
- **Probably related:** A reasonable temporal sequence of the event with administration of IP exists and based on the known response to the IP, known or previously reported adverse reactions to the IP or similar products, or in the PI's (or designee) clinical judgment the association of the event with the IP seems likely.
- **Definitely related:** A clinical event, including laboratory test abnormality, occurring in a plausible time relationship to IP administration, and which cannot be explained by concurrent disease or other drugs or chemicals.

If the relationship between the AE and the IP is determined to be “possible” “probable,” or “definitely”, the event will be considered to be “related” to the IP.

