9.6.4.1 Adverse Events

Adverse events will be coded to the MedDRA dictionary SOC and PT. They will be graded for severity according to Section 8.1.8. Only treatment-emergent AEs will be collected (ie, those after the start of IP administration). Adverse events will be reported using both age strata pooled, but selected AE analyses will be repeated for the separate age strata. All AE tabulations and participant listings will be based on the safety population.

Solicited AEs, unsolicited AEs, MAAEs, AESI, and SAEs will be summarized separately by treatment group and SOC, PT, and maximum severity for the safety population for both age strata combined. Only participants with at least one solicited AE observation (ie, any nonmissing values but excluding “not done/unknown”) will be summarized. Solicited AEs continuing beyond seven days after IP administration will be combined with the unsolicited AEs; a combined summary table of solicited and unsolicited AEs by treatment group and SOC, PT, and maximum severity will also be provided for the safety population for both age strata pooled.

Additional AE displays will include the following:

- Solicited AEs \geq Grade 3
- Treatment-related (“possibly”, “probably” or “definitely”) solicited AEs
- Solicited AEs: day of first onset, duration, day postinjection, and occurrence of at least one solicited AE by category (local, systemic)
- Unsolicited AEs \geq Grade 3
- Treatment-related (“possibly”, “probably” or “definitely”) unsolicited AEs

- Medically attended AEs
- Treatment-related MAAEs
- AEs leading to study discontinuation
- Fatal AEs, if any
- Treatment-related (“possibly”, “probably” or “definitely”) SAEs

Separate participant data listings of solicited and unsolicited AEs sorted by participant identifier and AE start date will be generated. Diary compliance will not be summarized.

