### **9.2 Adverse Events**

The safety of PXVX0317 in healthy adult participants  $\geq 65$  years of age is evaluated using solicited AEs occurring from IP administration on Day 1 through Day 8, unsolicited AEs through Day 29, and AESI and SAEs and MAAEs through Day 183 EOS. AEs are coded to SOC and PT according to the MedDRA dictionary per Section 5.8. They are coded for severity according to Section 5.9 and Appendix II. Only treatment-emergent AEs are summarized (i.e., excluding those after a participant has given informed consent, but before vaccination). See Section 6.3 for definitions.

Solicited AEs, unsolicited AEs, AESI and SAEs and MAAEs are summarized separately by treatment group and maximum severity for the safety population for both age strata combined. Separate participant data listings of solicited and unsolicited AEs sorted by participant identifier and AE start date are generated.

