### **9.2.1 Overall Summary of Solicited and Unsolicited Adverse Events**

A high-level summary of solicited and unsolicited AEs combined reviews the frequency counts and percentages of participants by treatment group reporting AEs in each of the following categories:

- Any AE and any AE  $\geq$ Grade 3
- Any solicited AE and any solicited AE  $\geq$ Grade 3
- Any treatment-related solicited AE and any treatment-related solicited AE  $\geq$ Grade 3
- Any unsolicited AE and any unsolicited AE  $\geq$ Grade 3
- Any treatment-related unsolicited AE and any treatment-related unsolicited AE  $\geq$ Grade 3
- Any SAE
- Any treatment-related SAE
- Any AE leading to study discontinuation
- Any fatal AE
- Any AESI (see definition in Section 6.3)
- Any MAAE and any treatment-related MAAE

In addition, summaries of combined solicited and unsolicited AEs by SOC, PT and highest reported severity are provided for the following populations:

- Safety population, both age groups
- Safety population by age strata
- Safety population by sex
- Safety population by race group
- Safety population by ethnicity

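### SAP 6.3 leaves definitely related events out of its definition of a related adverse event, contrary to Protocol 8.1.9

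*SAP*

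**What the plan says.** Protocol 8.1.9 defines four causality levels: unrelated, possibly, probably and definitely related. It then states that where the relationship is "determined to be “possible” “probable,” or “definitely”, the event will be considered to be “related” to the IP". Protocol 9.6.4.1 names the same three levels for the related solicited AE, unsolicited AE and SAE displays; the solicited entry reads "Treatment-related (“possibly”, “probably” or “definitely”) solicited AEs".

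Solicited AEs use the same scale. Protocol 3.2.9 has the investigator judge their causality under Section 8.1.9, and the result "will be recorded as a separate source document and will be entered on the solicited AE eCRF". SAP 2.2 says relationship is assessed for solicited AEs as it is for unsolicited ones.

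In SAP 6.3 a related AE "is defined as one that is “probably” or “possibly” related to IP per investigator assessment on the eCRF". If some occurrences of an AE have no recorded relationship, the closest relationship among the remaining occurrences is used. If the only occurrence has none, "then that event is assumed to be related in order to be conservative".

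SAP 9.2 directs the reader back with "See Section 6.3 for definitions". SAP 9.2.1 and 9.2.2 call for treatment-related displays, for example "Any treatment-related solicited AE and any treatment-related solicited AE" at Grade 3 or higher, and give no definition of their own. SAP 9.2.3, on unsolicited AEs, sets the threshold at possibly related or stronger.

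**The concern.** SAP 6.3 gives a closed list of two labels where the protocol has three, and the missing label is the strongest attribution an investigator can make. Protocol Section 9 calls itself a summary and leaves the details to the SAP, so 6.3 is the text a programmer would implement and a validator would check against. Independent double programming from 6.3 would reproduce the omission and not detect it.

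Treatment-related tables are where a reader looks for reactogenicity and harm that investigators attribute to the vaccine. As written, they could omit the events attributed most firmly while including events with no attribution.

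**Working it through.** No published figure needs reproducing. The check compares the definitions and counts the displays that depend on them.

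**Step 1: what each text counts as related**

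| Investigator's rating | Protocol 8.1.9 | SAP 6.3, read literally | SAP 9.2.3 (unsolicited AEs only) |
|---|---|---|---|
| Unrelated | no | no | no |
| Possibly | yes | yes | yes |
| Probably | yes | yes | yes |
| Definitely | yes | **no** | yes |
| Missing, only occurrence | not addressed | yes | not addressed |

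The protocol counts 3 of 4 levels and SAP 6.3 counts 2 of 4. The difference is exactly the definitely related events.

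The missing-data rule inherits the gap. If one occurrence is missing and another is rated definitely, the closest remaining relationship is definitely, which 6.3 does not count. A lone missing rating is counted.

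**Step 2: where the flag is used** (SAP 9.2.1 and SAP Appendix I)

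| Event type | Tables | Rows in 14.3.2.1 | Other SAP text |
|---|---|---|---|
| Solicited | 14.3.2.4, 14.3.2.5.2, 14.3.2.6.2 | 2 (any; Grade 3 or higher) | none restores definitely |
| Unsolicited | 14.3.5.5, 14.3.5.6 | 2 (any; Grade 3 or higher) | 9.2.3 conflicts with 6.3 |
| SAE | 14.3.5.8 | 1 | 9.2.3 arguably conflicts, since it places SAEs among unsolicited AEs |
| MAAE | 14.3.5.12 | 1 | 9.2.3 arguably conflicts |

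Tables: 3 + 2 + 1 + 1 = 7. Rows: 2 + 2 + 1 + 1 = 6.

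**Step 3: size**

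Let *d* be the share of protocol-related events rated definitely. Ignoring missing ratings, a literal 6.3 count captures 1 − *d* of them, so the shortfall is *d*. The documents give no value for *d*: the shortfall is 0% if *d* = 0 and 100% if *d* = 1.

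Counts of participants need not fall by the same share. If the flag is set occurrence by occurrence, a participant leaves an any-related row only when none of their qualifying events is rated possibly or probably, or is counted as related because the rating is missing. In a table by maximum severity, a participant may instead move to a lower grade.

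**The case against.** The strongest reply is that this is a drafting slip with little consequence. Nothing suggests that the sponsor meant to exclude definitely related events. The protocol spells out all three levels, SAP 9.2.3 agrees with it, and a closest-relationship rule assumes that stronger attribution counts for more. The SAP introduction says that some derivation details sit in programmer's notes in the table shells, which are not among the documents, so the working specification may already be correct. Solicited AEs that are serious, medically attended or ongoing after Day 8 are also recorded as unsolicited (SAP 9.2.2), which brings them under the wording of 9.2.3. Safety endpoints are reported for information only, and every event type is also tabulated regardless of relationship.

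Much of this is fair. It is probably a slip, the harm is conditional, and the stakes are limited. But unseen shells cannot be assumed to override a stated definition. SAP 2.2 governs how relationship is assessed, not which ratings are counted as related. The 9.2.2 route also leaves short-lived, non-serious, non-attended reactions with only 6.3. The missing-plus-definitely case is the same omission followed through, not a second defect.

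**Conclusion.** The concern holds. SAP 6.3 contradicts Protocol 8.1.9 and 9.6.4.1, and for unsolicited AEs it contradicts SAP 9.2.3. Applied literally, it gives wrong counts wherever an event is rated definitely related. The solicited displays are the clearest case, with three tables and two summary rows that no other SAP text corrects.

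The undercount rests on two assumptions: that the eCRF offers definitely as a rating, which Protocol 8.1.9 and 3.2.9 imply although the eCRF is not in the documents, and that the program follows 6.3 as written. Its size is unknown and may be zero.

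The overall incidence endpoints (solicited and unsolicited AEs, SAEs, MAAEs, AESI) do not depend on relatedness and are unaffected, and all SAEs are still tabulated and listed. The coprimary analyses, alpha and power do not change. It should be fixed, because the correction is trivial and only restores the protocol's own rule.

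**What to change.** Reword the definition in SAP 6.3 so that an AE counts as related when the investigator rates it possibly, probably or definitely related to the investigational product on the eCRF. Leave the rule for missing relationships unchanged; it then works as intended.

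Have SAP 9.2.3 refer to that definition instead of stating its own threshold. Its present wording already agrees with the protocol, so this step only secures a single definition.

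Apply the one flag to the six related rows of Table 14.3.2.1 and to Tables 14.3.2.4, 14.3.2.5.2, 14.3.2.6.2, 14.3.5.5, 14.3.5.6, 14.3.5.8 and 14.3.5.12. Confirm that the eCRF field, the shell notes and the program all carry the third level.

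The cost is one word in 6.3, one cross-reference in 9.2.3 and a check of the programmed flag.

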### 6.5.1 Missing or Partial Dates for Solicited Adverse Events

Solicited adverse events are collected from IP administration on Day 1 until Day 8 using an electronic diary (e-diary) or paper diary. In the case where a participant has all eight diary entries present and a single entry is missing a date (or has a partial date), then the missing date is assumed to be the date of the missing diary entry for that participant.

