### **9.2.2 Solicited Adverse Events from Day 1 until Day 8**

Solicited AEs recorded daily in the e-diary or paper diary until Day 8 include local (i.e., pain, redness, and swelling) and systemic reactions (i.e., fever, chills, fatigue, headache, myalgia, arthralgia, and nausea). In addition, solicited AEs ongoing after seven days post-injection (Day 8) and those that are serious or MAAEs are also recorded as unsolicited AEs. Severity of solicited AEs is assessed by the investigator in the same manner as unsolicited AEs.

Frequencies and percentages of participants experiencing each solicited AE are presented by maximum severity and by treatment group. The following summaries of solicited AEs are produced:

- Solicited AEs by maximum event severity, for each event and for any event
- Solicited AEs of severe (Grade 3) or higher severity, for each event and for any event

- Treatment-related solicited AEs by maximum event severity, for each event and for any event
- Day of first onset of solicited AEs, for each event and any event
- Duration of solicited AEs, for each event and any event
- Solicited AEs by day post-injection for each event and for any event

Occurrence of at least one AE by category (local, systemic) for solicited AEs are also included.

The denominator for solicited AE tables comprises only those participants with at least one diary observation (i.e., any non-missing values but excluding “Not done/unknown”), at least one diary observation for a given symptom, or at least one diary observation for a given day, as applicable. ***Note that an elevated in-clinic temperature assessment as part of 30-min post-vaccination vital signs does not count as a solicited AE, as vital signs data are summarized separately.***

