#### **9.2.3 Unsolicited Adverse Events from Day 1 through Day 29**

All unsolicited AEs occurring during the specified collection period in the study are recorded, regardless of their assessment of relatedness by the investigator. Unsolicited AEs include also those solicited AEs ongoing after seven days post-injection (Day 8), AESI, and SAEs.

All reported unsolicited AEs are summarized by treatment group according to MedDRA SOC, PT and highest reported severity. When an unsolicited AE occurs more than once for a participant, the maximum severity and closest relationship to treatment is counted. The unsolicited AE analysis includes unsolicited AEs judged by the investigator as at least possibly related to IP.

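### SAP 6.3 leaves a diary-only, solicited-type AE with new onset on Days 9–29 out of every summary table when it is neither serious nor medically attended

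*SAP*

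**What the plan says.** SAP 6.3 sorts AEs by how they were collected. Solicited AEs "are defined as those collected in the electronic e-diary or paper diary". Unsolicited AEs "are defined as those AEs not listed in the e-diary or paper diary but collected in the EDC".

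Each class then has a late-onset exclusion:
- Solicited: "solicited AEs starting on Day 9 or later will be excluded from tabulations, with the exceptions of AESI and SAEs", followed by a pointer, "see Section 9.2.2 for solicited events collection details".
- Unsolicited: "unsolicited AEs starting on Day 30 or later that are not SAEs, AESI, or MAAEs are excluded from tabulations".

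Two SAP sections move some solicited events into the unsolicited tables:
- SAP 9.2.2: "solicited AEs ongoing after seven days post-injection (Day 8) and those that are serious or MAAEs are also recorded as unsolicited AEs".
- SAP 9.2.3: "Unsolicited AEs include also those solicited AEs ongoing after seven days post-injection (Day 8), AESI, and SAEs".

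The protocol has matching rules for persisting symptoms. Under 3.2.9 they go on the AE eCRF once the solicited period is over, and under 9.6.4.1 they are pooled with the unsolicited AEs.

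The incidence of unsolicited AEs through Day 29 is a listed safety endpoint (Protocol 3.3.1; SAP 3.2).

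**The concern.** The exclusion in SAP 6.3 applies to tabulations in general, not only to the solicited tables. An event removed by that sentence is therefore gone from every summary unless another rule brings it back, and the transfer rules were written for events that began in the diary period and persisted. They say nothing about a symptom on the solicited list that first appears after Day 8, unless it is serious, an AESI or medically attended.

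The result is a one-day break. Fatigue that starts on Day 8 and persists is counted as solicited and again as unsolicited. Fatigue entered in the diary as starting on Day 9 is counted nowhere. What is at stake is the completeness of the AE summaries for the rest of the Day 29 collection period.

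**Working it through.** No calculation decides this point. The check traces each kind of diary-recorded solicited event through the rules.

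**Inputs.** The two definitions and two exclusions in SAP 6.3; the transfer rules in SAP 9.2.2 and 9.2.3 and Protocol 3.2.9 and 9.6.4.1; the MAAE definition in SAP 6.3; the table list in SAP Appendix I.

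**Trace.**
1. Onset by Day 8, resolved by Day 8: solicited tables.
2. Onset by Day 8, ongoing after Day 8: solicited tables, and also unsolicited tables under SAP 9.2.2 and 9.2.3.
3. Onset on Day 9 or later, SAE or AESI: kept by the exception in SAP 6.3.
4. Onset on Day 9 or later, MAAE that is neither an SAE nor an AESI: not named in the SAP 6.3 exception or in the 9.2.3 list, but carried over by 9.2.2 and tabulated under 9.3.4.
5. Onset on Days 9–29, not serious, not medically attended, recorded only as a diary event: removed by SAP 6.3 and restored by none of the four transfer rules.

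Case 5 is the gap. It spans 29 − 9 + 1 = 21 days of the unsolicited AE period.

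**Can case 5 occur?** The diary is planned to stop at Day 8. SAP 6.5.1 treats a complete diary as one in which the participant "has all eight diary entries present and a single entry is missing a date", and Protocol 8.1.6 gives seven days after vaccination. Protocol 3.2.9, however, sets seven days as a minimum. The diary is collected at Visit 3 (Day 15, −1/+3, so Days 14 to 18), and the Visit 3 list in Protocol 6.4 still includes solicited AE evaluation. Late entries are therefore possible but stray.

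**Events entered only on the AE eCRF.** These are most naturally unsolicited and counted. The SAP 6.3 definition is loose here, because it can refer either to the symptoms printed in the diary or to the entries made in it. On the first meaning, a fatigue with onset on Day 9 and recorded only on the eCRF would not fit the unsolicited definition either.

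**Outputs that would omit a case 5 event.** From SAP Appendix I: unsolicited tables 14.3.5.1 to 14.3.5.6, so up to 6; combined solicited-and-unsolicited tables 14.3.2.1 (1) and 14.3.3.1 to 14.3.3.5 (5), so up to 1 + 5 = 6. Tables 14.3.5.3 to 14.3.5.6 take only Grade 3 or higher, or treatment-related, events, so a mild unrelated event would be missing from fewer. These counts show where an event would be absent; they do not say how many events there are.

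**The case against.** **It is a deliberate window rule.** SAP 6.3 says diary entries were intended for Days 1 to 8, and any fixed window produces a break at its edge. This stands as a reason to keep late events out of the solicited tables. It does not explain why they should be absent from all tables while AEs are still being collected.

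**The event may not be unsolicited at all.** Protocol 3.2.10 describes unsolicited AEs as those the diary does not list. On that definition a diary-recorded event is solicited, and the solicited endpoint stops at Day 8. Protocol 8.1.7 is broader and takes in anything the investigator discovers. Visit 3 also combines diary review with unsolicited AE evaluation, so a stray entry may well reach the AE eCRF and be counted. This stands. A reader might infer that the Day 29 unsolicited endpoint is certainly under-counted, but the documents support only a conditional loss, for events that never leave the diary record.

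**Medically attended events are safe.** Because the SAP 6.3 exception names only AESI and SAEs, a reader might infer that a medically attended fever or headache starting on Day 10 is lost. The documents do not support that. SAP 6.3 takes MAAE status from a question on the AE eCRF, so such an event already has an eCRF record. SAP 9.2.2, to which the exclusion itself points, carries it over, the unsolicited rule in 6.3 keeps MAAEs even after Day 29, and 9.3.4 tabulates them to Day 183. What remains is an editorial mismatch with the 9.2.3 list.

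**Conclusion.** The gap is real but narrow, and its severity is minor. As written, SAP 6.3 keeps out of every summary table a solicited-type event that meets all of these conditions: new onset on Days 9–29, not serious, not medically attended, and recorded only as a diary event. The conclusion assumes that the programmer applies the exclusion literally and that the event has no AE eCRF record.

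The number of affected events cannot be derived from the documents and is probably small. A reader might also infer a bias between the arms or a threat to the trial's success criteria. Neither follows: the rule is the same in both blinded arms, the participant listings in SAP 9.2 keep the events, and the safety endpoints are descriptive under Protocol 9.4.2 and SAP 6.4.2.

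**What to change.** Change the SAP before unblinding; the protocol needs no amendment.

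1. In SAP 6.3, replace the solicited exclusion with: *Events of a solicited type with onset after Day 8, whether recorded in the diary or on the AE eCRF, are not counted in the solicited AE tables; they are classified as unsolicited AEs and tabulated if onset is on or before Day 29, or through Day 183 if they are SAEs, AESI or MAAEs.*
2. Match the unsolicited definition in SAP 6.3 to this. State there that solicited events with onset by Day 8 that are ongoing after Day 8, serious, AESI or MAAE are also counted as unsolicited, so that the definition agrees with SAP 9.2.2 and 9.2.3 and Protocol 9.6.4.1.
3. Editorial only: name MAAEs in the SAP 9.2.3 list, to agree with 9.2.2 and 9.3.4.

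The cost is wording in two SAP sections and one reclassification step in programming. The diary events concerned are already collected. Unsolicited AE counts may rise slightly.
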